Assessment of Adverse Events. A standard operating procedure will be established which is followed to collect and deal with adverse events during the research project. In particular, adverse events will be systematically monitored both during the treatment phases, as well as 3 and 6 months following study completion. In particular, participants will respond to a side effect check list to detect any possible physiological reactions related to the drug administration. This will include series of open-ended questions asked by trained research staff regarding any adverse events that have occurred since the last visit or phone contact. Aside from open questions about pain experienced in various parts of the body, dizziness or light headedness, research staff will inquire about changes in thirst or urination, as OT can alter water concentration in the kidneys in rare cases. Additionally, during the 3 and 6 months follow up, participants will be asked to the WOMAC and PANAS questionnaires to assess pain and feelings. This report will be reviewed by the principal investigator and study physician in a timely fashion. Any serious untoward event, whether related or unrelated to the study drug or procedures, will be reported to the UF IRB and FDA immediately as per their regulations.

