Adverse events will be defined as any physical symptoms or side effects that began following administration of the study drug. All reported and observed adverse events will be tracked in a running adverse events participant log, which will contain information regarding dates, description, and severity. All adverse events will be coded using the most current version of the Medical Dictionary for Regulatory Activities (MedDRA). The number and percentage of participants reporting treatment-emergent adverse events will be tabulated by treatment, system organ class and MedDRA-preferred term. Treatment-emergent adverse events will be those adverse events that begin or worsened following the first dose of study drug. Adverse events will be further classified by severity and investigator-assigned relationship to study drug. All reported and observed adverse events will be tracked on a running adverse events log (specific to each subject and maintained in his/her study file) and will contain information regarding onset/offset dates, time course (i.e., single, sporadic), severity, action taken regarding study drug, relationship to study drug, and whether it meets FDA criteria for "Serious." Each reported event is reviewed by the principal investigator and the study physician in a timely fashion. Additionally, the principal investigator reviews all adverse events recorded in each participant's log at the conclusion of study participation.

In Case of Emergency. Participants will have 24-hour access to emergency care and will be provided with a means of contacting the on-call study doctor and research staff. Participants will be informed and encouraged to contact the study physician and study staff immediately with medical concerns or unusual reactions. Participants will also be informed of the closest Emergency Department location to their residence.

Data and Safety Monitoring Plan. A Data Safety Monitoring Plan will be in place. In particular, the following procedures will be implemented to ensure data and participant safety. Study progress and safety will be reviewed by the principal investigators in collaboration with [name], M.D., the study MD, and [name], M.D., Ph.D., the sponsor of the IND and consultant on the project.

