We will stop the intervention if 30% or more of the participants in the OT condition report 10 or more (out of forty-four) of the side effects at moderate to severe levels over more than 2 weeks as acquired during the weekly check in phone calls during the intervention phase. Data collected prior to stop of

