intervention will be used for analysis. All participants who went through the intervention phase of the study will be followed up by phone calls at multiple time points to ensure safety; every 7 days during the intervention, 7 days post intervention, 3 months post intervention, and 6 months post intervention. Progress reports, including participant recruitment, retention/attrition, and adverse events will be provided to an Independent Safety Monitor(s) for reviews on a bi-annual basis. The Independent Safety Monitor(s) for this study will consist of an established senior investigator not associated with our study. A study end report will be compiled and will include a list and summary of adverse events. In addition, this report will address: (1) whether adverse event rates are consistent with pre-study assumptions; (2) reason for dropouts from the study; (3) whether all participants met entry criteria; (4) whether continuation of the study is justified on the basis that additional data are needed to accomplish the stated aims of the study; and (5) conditions whereby the study might be terminated prematurely. The annual report will be signed by the Independent Safety Monitor and will be forwarded to the IRB, NIH, and FDA. The Independent Data Safety Monitoring Plan will also require that all significant serious adverse events that may be possibly related to the study participation will be reported to the IRB, FDA, and NIH within 48 hours of the principal investigators learning of the event. In addition, any unanticipated serious adverse events that may increase the risk of the research for participants or potential participants will be reported to the IRB and the NIH within 48 hours of the principal investigators being informed about the event. This study will be stopped prior to its completion if: (1) the intervention is associated with adverse effects that significantly impact the risk-benefit ratio, (2) study recruitment or retention becomes futile, (3) any new information becomes available during the trial that necessitates stopping the trial; or (4) if independent safety monitor indicates that stopping the trial is necessary due to adverse event frequency or severity.

ClinicalTrials.gov Requirements. In accordance with Public Law 110-85 and NIH guidelines, the proposed research will be registered with ClinicalTrials.gov prior to commencement of study procedures involving participants.

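### Neither 48-hour serious-event report names the Independent Safety Monitor, so the person behind stop criterion (4) may wait up to about 26 weeks for notice of such events

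*Combined protocol and SAP*

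**What the plan says.** All references are to Section 7 of the UCOPE protocol unless stated otherwise.

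**The stop power.** The Data and Safety Monitoring Plan lists four grounds for ending the study early. The fourth applies "if independent safety monitor indicates that stopping the trial is necessary due to adverse event frequency or severity". The monitor "will consist of an established senior investigator not associated with our study".

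**What the monitor receives.** Progress reports covering recruitment, retention and "adverse events will be provided to an Independent Safety Monitor(s) for reviews on a bi-annual basis". The monitor also signs an annual report.

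**Who receives expedited reports.**
- Assessment of Adverse Events: any serious untoward event, related or not, "will be reported to the UF IRB and FDA immediately as per their regulations".
- Data and Safety Monitoring Plan, first category (significant serious events possibly related to participation): "reported to the IRB, FDA, and NIH within 48 hours of the principal investigators learning of the event".
- Data and Safety Monitoring Plan, second category (unanticipated serious events that could raise participants' risk): these "will be reported to the IRB and the NIH within 48 hours of the principal investigators being informed about the event".

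The monitor is named on none of the three. Individual events are reviewed by the principal investigator and the study physician. Ongoing safety review is by the principal investigators with the study physician and the IND sponsor.

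**The concern.** Criterion (4) is the only one of the four stop criteria that names an independent decision maker. Severity is part of its wording, and a severity judgement can turn on a single event. Yet the serious events most likely to prompt that judgement go quickly to everyone listed except the person who holds the power. If the protocol is followed to the letter, the monitor need not hear of such an event until the next periodic report.

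What is at stake is the timing of one trial-level safeguard. While the monitor waits, other participants continue through treatment, washout and the second treatment period. The estimate of the treatment effect is not affected.

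**Working it through.** **Inputs**
- Adverse-event reports to the monitor: bi-annual, read as 2 per year (Data and Safety Monitoring Plan).
- Expedited limit: 48 hours from the investigators learning of the event (same place).
- Crossover schedule: 4 weeks of treatment, 4 weeks of washout, 4 weeks of treatment (Section 6, Research Plan).
- Phase-two baseline visits: up to 4, or 6 with MRI (Section 6, Phase Two Procedures). No interval is given. I assume they take 0 to 6 weeks, that is, at most one visit per week.

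**Step 1: the monitor's wait as written.** The longest gap is 52 / 2 = 26 weeks (365.25 / 2 = 182.6 days). The wait from the day the investigators learn of an event therefore runs from 0 to about 26 weeks. If events fall evenly between reports, the mean is 26 / 2 = 13 weeks (182.6 / 2 = 91.3 days).

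If bi-annual meant every two years, the gap between progress reports would be about 24 months. Twice a year is the more natural reading beside an annual signed report, and it gives the smaller figure.

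**Step 2: the wait of the listed recipients.** 48 hours = 2 days. The weekly calls mean that the investigators may themselves learn of an event up to about 7 days late, but this adds equally to both waits.

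**Step 3: compare with the participant schedule.** Treatment, washout and treatment take at least 4 + 4 + 4 = 12 weeks. Adding the assumed 0 to 6 weeks for phase-two baseline visits gives 12 to 18 weeks. With events spread evenly over a 26-week gap:

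| Wait longer than | Share of event times |
|---|---|
| 12 weeks | (26 − 12) / 26 = 14 / 26 = 54% |
| 18 weeks | (26 − 18) / 26 = 8 / 26 = 31% |

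So another participant could complete the whole sequence before the monitor must be told, but only for part of the range. Each participant receives oxytocin in just 4 of those weeks.

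**Step 4: what adding the monitor changes.**

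| Event type | Longest wait now | Longest wait with the monitor added |
|---|---|---|
| Either 48-hour category | about 26 weeks | 2 days |
| Other serious events | about 26 weeks | about 26 weeks |
| Non-serious adverse events | about 26 weeks | about 26 weeks |

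**Step 5: how often it would matter.** The documents give no serious-event rate, so this cannot be computed. Section 7 reports no consistent side effects in over 100 older participants given the same compound at the same dose and frequency. It also cites three significant reactions to intranasal oxytocin in the literature, one after 4 weeks of use. The risk is probably low, but the protocol itself recognises it.

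**The case against.** **Silence is not exclusion.** The monitoring plan says "the following procedures will be implemented to ensure data and participant safety", but introduces these as particular measures within a wider plan, so the list need not be closed. An adverse-event operating procedure is also to be established. Either document might name the monitor, and nothing bars earlier contact. This stands in part. A reader might infer that no rapid route to the monitor is planned; the documents show only that this protocol states none. They do set out recipient lists, however, and following those lists leaves the monitor uninformed.

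**Independent eyes already see these events.** The IRB and NIH, and the FDA for the first category, are told within 48 hours, and the UF IRB and FDA are told immediately of any serious event. This stands. A reader might infer that independent oversight as a whole is delayed by six months; it is not.

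**Other safeguards act sooner.** Section 6 provides for individual discontinuation and for weekly calls with escalation of moderate or severe symptoms. Section 7 adds safety laboratory tests after withdrawal for possible drug effects, and unblinding for severe side effects. At trial level there are criteria (1) and (3) and the side-effect rule: "We will stop the intervention if 30% or more of the participants in the OT condition report 10 or more" of forty-four listed side effects at moderate to severe levels for more than two weeks. This stands too, so the affected participant's care is not delayed. But the side-effect rule cannot be met by one or a few serious events, and criteria (1) and (3) name no decision maker.

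**The remedy is partial.** Criterion (4) also covers frequency, and single-event reports do not supply rates. That is correct, and it limits what the fix can claim.

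**Conclusion.** The point holds in a limited form. As this protocol is written, the monitor's required notice of serious events in the two 48-hour categories comes 0 to about 26 weeks after the investigators learn of them. The mean is about 13 weeks if events fall evenly. The 26-week figure is a worst case: it needs an event that becomes known just after a report.

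Two stronger readings are not supported. One is that any safety stop could be held up for six months; other stop routes, the IRB and the regulators can act at once. The other is that naming the monitor on the two reports would bring every serious event to the monitor within 2 days; it would do so only for the two categories.

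The conclusion rests on reading bi-annual as twice a year, and on no separate plan or procedure already adding the monitor. The comparison with the 12-to-18-week sequence also rests on the assumed 0 to 6 weeks for phase-two visits. No harm is shown and the trial's inference is untouched. This is a cheap safety improvement worth making.

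**What to change.** In the UCOPE Data and Safety Monitoring Plan, name the Independent Safety Monitor as a recipient of both 48-hour serious-event reports. Add a sentence saying that the monitor may act on criterion (4) between scheduled reviews. Leave the immediate report to the UF IRB and FDA, the bi-annual progress reports and the annual signed report as they are. If a separate monitoring plan or operating procedure already includes the monitor, bring the protocol text into line with it.

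The cost is one more recipient on two reports that are already required, and occasional unscheduled review by the same monitor. Sample size, analysis and participant burden do not change.

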intranasal OT or P and will be contacted once a week for assessment of adverse effects and for download of the smartwatch/ring data. As in our pilot study, during the last week of each intervention period, up to four assessment sessions will follow that will be identical to the baseline sessions. On the mornings of assessment days, participants will not apply the OT/P nasal spray, to avoid confounding of acute and chronic effects.

To increase flexibility and reduce participant burden, portions of the study (including the ICF) may be conducted remotely via phone calls, UF Zoom and/or online (RedCap). Parts of the study that cannot be conducted remotely, will be conducted in a single visit pre- and post- the intervention period and as needed study portions may be dropped. These portions include but are not limited to: blood draw and urine sample, Neuroimaging, sensory testing, and questionnaires. Questionnaires and /or surveys with sensitive questions, such as childhood trauma or suicidal ideations, will continue to be administered in person.

Participants: Based on power-analytic considerations, we plan to enroll a total of 160 individuals of both sexes (approx. 50% male) from various ethnicities. This sample size includes a 20% attrition rate. Older adults over 45 years of age who meet American College of Rheumatology clinical criteria for knee OA⁷⁸ and/ or back pain of at least six months duration, experience pain on more days than not, with moderate pain at baseline (i.e., > 3/6 in the VDS), and who have elevated levels of plasma IL-6 (>2.5 pg/ml) will be considered for participation. We will also recruit 160 control individuals (80 older adults over 45 years of age without knee osteoarthritis pain and 80 younger controls 18 to 30 years of age). Both community-based and clinic-based recruitment methods established in our labs will be utilized. We will also utilize IRB approved registries to contact potential participants.

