
Rigor of the prior research. There are noted gaps and weaknesses of the prior research that need to be addressed in order to move this field forward that this application plans to address. Historically, the consideration of pain impact has been overlooked, likely leading to inconsistent results among the literature observing the

relationship between AD/ADRD and chronic pain. Additionally, studies implicating lifestyle factors such as nutrition as a possible mechanism influencing the relationship between pain and cognitive disease have not been completed, despite evidence of nutrition status influencing on both disease states independently. Finally, the examination of epigenetics (influenced by nutrition) such as DNA methylation and epigenetic/cellular aging as a common mechanism driving both pain and AD/ADRD in tandem has not been appreciated. This proposal not only will provide the candidate with the opportunity to train in an outstanding research environment, but also allow her to contribute to filling the gaps in the literature that will allow the field to progress towards solutions to solve the complex problems seen in chronic pain and AD/ADRD.

5. Specific Aims

Specific Aim 1: Determine the association among DII, epigenetic clocks/cellular aging and cognitive function middle-age and older adults with low-impact pain, high-impact pain and pain free controls.

Hypotheses 1a-d: Individuals with chronic pain will (H1a) have a more positive/inflammatory DII, which will be associated with (H1b) accelerated epigenetic aging and (H1c) greater cognitive impairment. These associations will be more significant in the high-impact pain group compared to those with (H1d) low-impact pain and pain-free controls.

6. Research Plan

We propose a cross-sectional, observational study design that will assess the relationship between pain, cognition and dietary pattern in older adults with and without symptomatic knee OA pain. This will be completed in 2 experimental sessions approximately one week apart. After initial screening, eligible participants will undergo the sessions (health and sensory sessions) for collection of clinical, functional (physical, cognitive, emotional), QST, and blood-based biomarker data lasting 2-3 hours.

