Participants: *This study will be ancillary to one of primary mentor [name] ongoing studies, significantly increasing feasibility.* Thus, participant data for this phase will be collected from **previously obtained** experimental pain outcomes (QST), cognitive outcomes, self-reported demographic variables (age, sex/gender, race/ethnicity, education, household income), other covariate (depression, anxiety, smoking, body mass index) information due to their known influence on pain outcomes, as well as previously collected and stored blood samples (n=50). Additionally, **we plan on enrolling 40 more participants** into the PANDA study that do not meet the inclusion/exclusion criteria of the parent UCOPE study. Based on power-analytic considerations, we plan to obtain data for a total of 90 individuals of both sexes (approx. 50% male) from various ethnicities. This sample size includes a 20% attrition rate. Older adults over 55 years of age who meet American College of Rheumatology clinical criteria for knee OA⁷⁸ of at least six months duration, experience pain on more days than not, with moderate pain at baseline (i.e., > 3/6 in the VDS), and who have elevated levels of plasma IL-6 (>2.5 pg/ml) will be considered for participation. Both community-based and clinic-based recruitment methods established in our labs will be utilized. We will also utilize IRB approved registries to contact potential participants.

Exclusion criteria will align with study and safety requirements related to 1) **Pain testing:** participants will be excluded if they have concurrent medical or arthritic conditions that could confound symptomatic knee OA-related outcomes or coexisting disease that could preclude successful completion of the protocol including: systemic rheumatic condition (e.g. rheumatoid arthritis, systemic lupus erythematosus, fibromyalgia); a history of clinically significant surgery to the index knee; uncontrolled hypertension (>150/95); poorly controlled diabetes (HbA1c>7%); cardiovascular or peripheral arterial disease; serious psychiatric disorder requiring hospitalization within the past twelve months or characterized by active suicidal ideation; diminished cognitive function that would interfere with completion of study procedures (i.e., MoCA score < 25)];⁸¹ and 2) **pregnant individuals will be excluded;** and 3) **enrolled in another interventional research study.**

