Dietary Inflammatory Index. The Dietary Inflammatory Index (DII) was developed to provide a quantitative means for assessing the role of diet in relation to health outcomes ranging from blood concentrations of inflammatory cytokines to chronic diseases. **For the K99 phase**, diet data has been previously collected in the form of a 24-hour food recall. To collect diet data, participants were asked to document food and beverages consumed, as well as supplements taken 24 hours prior to their visit. Assessments were conducted interview-style by a trained research assistant in order to probe deeper into the details of meals. Visual aids such as standard measuring cups, plates, and drink cups in various sizes etc. were provided to aid in accuracy. These data will then be entered into the Nutrition Data System for Research (NDSR) for nutrient analysis. Following quantification, nutrient values will be used to calculate DII score according to the instructions laid out by Hebert & Shivappa et al⁶⁵.

Vitamin A and D Analyses. In order to quantify serum Vitamin D levels, the Quantikine[®] Human Vitamin D BP immunoassay (R&D Systems) will be employed. To quantify Vitamin A levels, a Colormetric Human Vitamin A ELISA Kit (Novus Biologicals) will be used. Kit-specific protocols will be used during quantification.

Epigenetic Analyses. Details regarding the protocol for processing and analyzing epigenetic data published elsewhere^{66, 67}. In short, the raw data generated by Illumina EPIC array (.idat files) will undergo quality control and normalization prior to the calculation of DNAmGrimAge via an online calculator (dnamage.genetics.ucla.edu). The age-adjusted AgeAccelGrim variable will be calculated as the difference between chronological age and DNAmGrimAge and used throughout the analyses.

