Hypotheses and data-analytic strategy: Prior to the testing of proposed hypotheses, each variable will be carefully examined to identify missing values, statistical outliers, and violations of relevant assumptions (i.e., Durbin-Watson, Shapiro-Wilk). Sensitivity analyses would then be completed to examine differences in results between variables with missing data and those same variables with data imputation. A corrected threshold will be set to 0.05, two-tailed. Descriptive statistics will be computed and represented as percentages or means (standard deviations). Group differences (pain impact groups; Vitamin A and D clinical cutoff differences) among potential covariates of interest will be examined using a series of one-way analysis of variance tests (ANOVAs) with follow-up/post hoc Bonferroni corrections. All participants will be matched on race and sex due to their relationships with pain and cognitive outcomes. All statistical analyses employed in this study were performed using SPSS (IBM) version 28.0 (IBM; Armonk, NY). Specific to hypotheses 1a-d: Sequential hierarchical multiple regression models will be employed to investigate the extent to which the continuous DII variable is associated with (H1a) greater severity, duration, and frequency of experimental and clinical pain outcomes, (H1b) accelerated epigenetic aging, and (H1c) worse cognitive decline between individuals with and without pain. Analyses of Variance (ANOVAs) will be performed in order to examine differences in variables of interest between groups: high-impact chronic pain, low-impact pain, and pain free controls. Additionally, three separate sequential hierarchical regression models within each group will be used to examine the extent to which higher scores DII scores are associated with epigenetic aging and cognitive outcomes. Variables of interest (DII, epigenetic age, cognitive status) will be entered into *step 1* of the analysis, relevant clinical covariates (e.g., BMI, smoking) will be entered in *step 2* of the hierarchical regression models, and relevant demographic variables (i.e., age, race, sex, etc.) in *step 3* of the regression models. Finally, a modified Poisson-regression analysis will be performed to assess the relative risk of clinical cognitive impairment between pain impact groups.

7. Possible Discomforts and Risks

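### PANDA requires raised IL-6 of its pain participants, but the UCOPE controls, the only described source of pain-free people, have no IL-6 criterion; if they are the comparator, the group contrasts on DII and epigenetic age are confounded with selection on IL-6

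*Combined protocol and SAP*

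**What the plan says.** - **PANDA inclusion** (PANDA section 6, Participants). One rule is given: age over 55, knee OA, pain on more days than not, VDS above 3/6, "and who have elevated levels of plasma IL-6 (>2.5 pg/ml) will be considered for participation". The planned 90 are 50 with existing UCOPE data and stored blood plus 40 new enrolees who do not satisfy the UCOPE criteria. How the 50 divide between pain cases and controls is not stated.
- **Groups required.** PANDA's aim refers to "adults with low-impact pain, high-impact pain and pain free controls", and its design to "older adults with and without symptomatic knee OA pain". The analysis section plans ANOVAs to "examine differences in variables of interest between groups: high-impact chronic pain, low-impact pain, and pain free controls". No PANDA eligibility rule describes a pain-free participant.
- **UCOPE** (UCOPE section 6, Participants). The pain cohort carries the same IL-6 cut-off. The controls are "80 older adults over 45 years of age without knee osteoarthritis pain and 80 younger controls 18 to 30 years of age", with no IL-6 criterion.
- **Hypotheses** (PANDA section 5). People with chronic pain will "have a more positive/inflammatory DII, which will be associated with (H1b) accelerated epigenetic aging". H1a is therefore a group difference in DII, and H1b an association of DII with epigenetic aging.
- **Adjustment** (PANDA analysis section). Matching is on race and sex. BMI, smoking and demographic variables enter the regressions. IL-6 is not named.

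**The concern.** The two sides of the pain versus pain-free contrast appear to be selected differently on an inflammatory marker, and the outcomes are ones the plan itself ties to inflammation. The DII section says the index was built to assess the "role of diet in relation to health outcomes ranging from blood concentrations of inflammatory cytokines to chronic diseases", and the PANDA background links diet, immune activation, the epigenome and pain. If IL-6 correlates with DII or epigenetic age, choosing only high-IL-6 pain participants raises the pain group's mean on those outcomes even when pain makes no difference. A positive H1a, or a positive ANOVA on epigenetic age, could then reflect the entry rule.

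The same rule narrows the IL-6 range in both pain groups but not in the controls. That weakens within-pain-group associations that run through inflammation, which is the opposite effect on a different set of hypotheses.

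The clause looks carried over. In UCOPE, IL-6 is an outcome of an anti-inflammatory hypothesis. PANDA gives no drug, states no reason for the threshold, and retains other drug-trial text such as sampling before randomization. The clause also bars people with knee OA pain who failed UCOPE only on IL-6, an obvious recruitment pool.

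**Working it through.** **The plan's own figure.** 50 + 40 = 90, and 72/(1 - 0.20) = 90, so the total and the stated 20% attrition are arithmetically consistent. The power basis cannot be reproduced: PANDA gives no effect size, SD, target power or group sizes.

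**Where the comparator can come from.** The single rule requires knee OA and VDS above 3/6, so it admits no pain-free person. Followed literally, it leaves only the stored UCOPE data, and the only UCOPE cohort without knee OA pain is the controls. This is an inference; PANDA does not say it.

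**Inputs.** From the documents: the cut-off of 2.5 pg/ml, N = 90, two-tailed 0.05. Assumed, because the documents give none of them: IL-6 normal on a suitable scale; share q of pain candidates above the cut-off, 0.3 to 0.7; correlation r of IL-6 with the outcome, 0.1 to 0.4; no true group difference; a two-group comparison of pooled pain versus pain-free, with splits as shown.

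**Shift in the group mean.** Shift in SD units = r × λ, where λ = φ(c)/q and c = z(1 - q). λ is 1.159, 0.798 and 0.497 for q = 0.3, 0.5 and 0.7.

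Example, q = 0.5 and r = 0.3:
- λ = 0.3989/0.5 = 0.798; shift = 0.3 × 0.798 = 0.239 SD.
- Outcome variance in the selected group = 1 - r²λ(λ - c) = 1 - 0.09 × 0.637 = 0.943.
- With 60 versus 30, SE = √(0.943/60 + 1/30) = 0.2215.
- Rejection probability = 1 - Φ(1.96 - 0.239/0.2215) + Φ(-1.96 - 0.239/0.2215) = 0.19.

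| r | q | Shift (SD) | 60 vs 30 | 48 vs 24 | 65 vs 25 |
|---|---|---|---|---|---|
| 0.1 | 0.7 | 0.05 | 5.6% | 5.5% | 5.5% |
| 0.2 | 0.5 | 0.16 | 11% | 10% | 10% |
| 0.3 | 0.5 | 0.24 | 19% | 16% | 17% |
| 0.3 | 0.3 | 0.35 | 35% | 29% | 31% |
| 0.4 | 0.3 | 0.46 | 56% | 47% | 50% |

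The first two splits use the normal test above; 65 versus 25 uses the noncentral t with equal variances. The 48 versus 24 split is 60 versus 30 after 20% attrition. If r = 0 the shift is 0 and the rate stays at 5%. For scale, the difference detectable with 80% power at 60 versus 30 is (1.960 + 0.842) × √(1/60 + 1/30) = 0.63 SD.

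**Association of DII with aging (H1b).** Suppose IL-6 drives both, with correlations 0.3 and 0.5, so the unselected correlation is 0.15. At q = 0.5 the variance of IL-6 after truncation is 1 - 0.637 = 0.363. The correlation within the pain group is 0.15 × 0.363/√[(1 - 0.09 × 0.637)(1 - 0.25 × 0.637)] = 0.0545/0.890 = 0.06. With both correlations at 0.4, simulation (2 million draws) gives 0.16 unselected, 0.06 within the pain group and 0.12 pooled 2:1. If instead DII and aging independently raise IL-6 (0.4 each), the correlation goes from 0.00 to -0.11 within the pain group and -0.05 pooled. Both scenarios run against H1b.

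**One rule for all.** With the same cut-off in both groups (r = 0.3, q = 0.3 to 0.7), the simulated induced difference is at most 0.002 SD, provided the IL-6 distributions are otherwise alike.

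**The case against.** PANDA never says its pain-free group comes from the UCOPE controls. The 40 new enrolees are described only as failing the UCOPE criteria, which could be meant to include pain-free people. That stands, so the point has to be conditional. It does not remove the need to act: if the single rule is followed, no pain-free person can be newly enrolled, and if it is not, eligibility for that group is simply unwritten.

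The size rests on two quantities the documents do not give. At the mild end the rate is 5.5% against a nominal 5%, which is negligible. DII comes from one 24-hour recall, and measurement noise favours a low correlation. Adjustment for BMI and smoking may absorb part of the shift in the regressions, although the ANOVAs are not described as adjusted. The analysis section also turns H1a into a regression of pain outcomes on DII and leaves group differences to the ANOVAs, so the shift concerns H1a as worded in the aims, and those ANOVAs.

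Restricting every group to high IL-6 has its own problem. The plan places inflammation downstream of diet, so conditioning on IL-6 could remove a genuine dietary difference and can distort the DII-aging correlation, as the -0.11 above shows. This is why the added analysis should be confined to the group contrasts.

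Finally, PANDA is a cross-sectional ancillary study; nothing here touches the randomised oxytocin comparison.

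**Conclusion.** The point holds in conditional form. If UCOPE controls are the comparator and IL-6 correlates positively with DII or epigenetic age, the pain versus pain-free contrasts (H1a and the ANOVAs on DII and epigenetic age) are shifted towards a pain effect. Under the assumed ranges the shift is 0.05 to 0.46 SD, with a false-positive rate of about 5.5% to 50% at 65 versus 25 (up to 56% at 60 versus 30). Mid-range assumptions give at least double the nominal 5%.

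A reader might infer that the entry rule by itself would lead to H1a and H1b both being declared supported. The documents do not bear that out. H1b is an association, and truncation weakens or reverses it within the pain groups. The direction and size for H1a depend on a correlation and a selected share that are not given. For H1d, both pain groups are truncated alike, so only the part comparing high-impact pain with controls is clearly affected, and the effect there is adverse to the hypothesis.

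This is an inexpensive improvement to an ancillary study, worth making because nothing in the stated matching or covariates offsets the imbalance.

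**What to change.** In PANDA section 6, Participants:
- Delete the IL-6 requirement for the 40 new participants.
- State where the pain-free group comes from and what its eligibility criteria are.

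In the PANDA analysis section:
- Add a sensitivity analysis of the group contrasts only (H1a and the ANOVAs, not the H1b and H1c associations), applying one IL-6 rule in every group.
- Report that the stored pain cases were selected on IL-6 and, if UCOPE controls are used, that the controls were not.

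Cost: an amendment to one eligibility paragraph and one extra analysis. IL-6 is already among the planned assays for UCOPE controls and PANDA participants, and recruitment becomes easier. Downsides: the pain group is less enriched for inflammation; the asymmetry remains for the stored pain cases; and the restricted analysis uses fewer controls and conditions on a variable that may lie downstream of diet. It should be read as a check, not as the primary result.
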